9.2.2. Exclusion criteria

Patients meeting any of the following criteria will not be included in the study:

1. Exposed to any known teratogens from 3 months prior to ECD through the end of the relevant exposure window.

The exclusion period of 3 months is a conservative approach given the relatively short half-life of many teratogens. Exposure to teratogens will be assessed via the presence of NDCs or medical procedure codes (Healthcare Common Procedure Coding System [HCPCS]). The list of known teratogenic drugs used for exclusion and accompanying half-lives is provided in ANNEX 2. ADDITIONAL INFORMATION.

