9.2.5. Exposure windows

From the base population, qualifying pregnancies will be classified according to the COVID-19 treatment received during the following relevant exposure windows:

- First trimester exposure window
 - o Start date: ECD therapy-specific window
 - o End date: End of the first trimester

• Pregnancy exposure window

o Start date: ECD – therapy-specific window

End date: End of the pregnancy

As different COVID-19 therapies will have varying rates of elimination, the length of each relevant exposure window will be extended (prior to the ECD) by a corresponding therapy-specific window, based on the indicated treatment duration (plus a grace period for self-administered drugs) and the time to non-detectable concentration in the body (defined as 5x the clearance half-life). This ensures the capture of exposure to COVID-19 therapies administered or dispensed prior to the ECD but which remain in the body at ECD. Sections 9.2.6.1 and 9.2.6.2 describe the therapy-specific windows for each of the study therapies.

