9.5. Study size

The planned sample size incorporates several assumptions derived from published literature, including the following approximate prevalence of pregnancy outcomes:

- Under 1% of pregnancies result in stillbirth (FDA 2002)
- 14% of pregnancies result in SA or miscarriage (FDA 2002)
- 18% of pregnancies have historically been expected to end in induced termination (Jones et al. 2017)
- 3% of live born infants have a major birth defect in the US each year (March of Dimes 2015)
- 10% of live born infants are born preterm or SGA (CDC 2008, Ferré et al. 2016)

Based on these reference percentages, the following assumptions were made for sample size calculation:

- $\alpha = 0.05$
- Power=0.8
- 1:2 matching
- Outcome prevalence as cited above

Table 1 and Table 2 show the minimum required number of PAXLOVID-exposed pregnancies required to proceed to the secondary objective of comparative analyses. Comparative analyses will be conducted if the sample size to detect a RR > 2.0 is achieved for each outcome; target sample size may be achieved for some outcomes but not others.

To detect a RR > 2.0 at 80% power a minimum of 127 PAXLOVID-exposed pregnancies are required for SA, 251 for SGA and preterm birth, and 2,212 for stillbirth, the rarest of the outcomes (Table 1). A minimum of 938 PAXLOVID-exposed pregnancies during the first trimester are required for the primary outcome of MCM (Table 2).

Fewer PAXLOVID-exposed pregnancies are required to detect an RR of > 2.5 at 80% power: 63 for SA, 127 for SGA and preterm birth, and 1,142 for stillbirth. For MCM, the minimum number of pregnancies with PAXLOVID exposure during the first trimester is 482. These estimates are based on 1:2 matching; however, the analyses for this study will utilize IPTW for confounding adjustment. Sample size calculations are based on 1:2 matching as a conservative estimate due to the retention of all eligible pregnancies in IPTW. Power for the analysis of induced termination will be similar to that for SA. The majority of pregnancies end in livebirth; therefore, power is expected to be adequate for this outcome.

Table 1. Sample Size Required for 80% Power to Detect Relative Risks (As or More Extreme) for Pregnancy Outcomes, with 1:2 Matching

Outcome	Prevalence of Outcome	RR	PAXLOVID-Exposed Pregnancies with Observed Outcomes Needed*	PAXLOVID-Exposed Pregnancies Needed**
SA	14%	2	101	127
		2.5	50	63
Stillbirth	1%	2	1,769	2,212
		2.5	913	1,142

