ANNEX 2. ADDITIONAL INFORMATION

Teratogenic drugs used for exclusion

Teratogenic Drugs	Half-life Range	Reference(s)
angiotensin-converting- enzyme (ACE) inhibitors	<1 to 17 hours	Sanders et al. 2011
angiotensin II receptor blocker*	2 to 24 hours	Burnier 2001
carbamazepine	18 to 65 hours	Bertilsson 1978
chemotherapeutic drugs for the treatment of cancer	Variable (maximum: 215 hours [mitoxantrone])	Ehninger et al. 1986
dolutegravir	14 hours	Mulligan et al. 2018
fluconazole	20 to 50 hours	Brammer et al. 1990
isotretinoin	Up to 29 hours	Brazzell et al. 1982
lithium	Up to 3 days following continuous therapy	Goodnick et al. 1981
methotrexate	Up to 69 hours	Shen et al. 1978
methylene blue	Up to 24 hours	Peter et al. 2000
misoprostol	<1 hour	Davies et al. 2001
mitoxantrone	215 hours	Ehninger et al. 1986
mycophenolate	Up to 17 hours	Fulton et al. 1996
penicillamine	Up to 6 days following treatment cessation	Munro et al. 1997
phenobarbital	Up to 132 hours	Nelson et al. 1982
phenytoin	Up to 42 hours	Ahn et al. 2008
teriflunomide	18 to 19 days	FDA 2012
thalidomide	<8 hours	Teo et al. 2004
topiramate	Up to 56 hours	FDA 1996
valproic acid	10 to 16 hours	Gugler et al. 1980
warfarin	Up to 40 hours	Walfisch et al. 2010

^{*} Exposure in 2nd or 3rd trimester

Codes for the identification of pregnancy and infant outcomes

All codes are ICD-10 diagnosis codes unless otherwise specified.

Pregnancy Outcomes

The pregnancy outcomes to be assessed are:

- SA
 - O02.1 Missed abortion

- O03.0 Genital tract and pelvic infection following incomplete spontaneous abortion
- O03.1 Delayed or excessive hemorrhage following incomplete spontaneous abortion
- O03.2 Embolism following incomplete spontaneous abortion
- O03.30 Unspecified complication following incomplete spontaneous abortion
- O03.31 Shock following incomplete spontaneous abortion
- O03.32 Renal failure following incomplete spontaneous abortion
- O03.33 Metabolic disorder following incomplete spontaneous abortion
- O03.34 Damage to pelvic organs following incomplete spontaneous abortion
- O03.35 Other venous complications following incomplete spontaneous abortion
- O03.36 Cardiac arrest following incomplete spontaneous abortion
- O03.37 Sepsis following incomplete spontaneous abortion
- O03.38 Urinary tract infection following incomplete spontaneous abortion
- O03.39 Incomplete spontaneous abortion with other complications
- O03.4 Incomplete spontaneous abortion without complication

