- HCPCS S0190 Mifepristone ORAL 200 mg
- HCPCS S0191 Misoprostal oral 200 mcg
- HCPCS S0199 Medically induced abortion by oral ingestion of medication including all associated services and supplies
- HCPCS S2260 Induced abortion, 17-24 weeks
- HCPCS S2262 Abortion for maternal indication, 25 weeks or greater
- HCPCS S2265 Induced abortion, 25-28 weeks
- HCPCS S2266 Induced abortion, 29-31 weeks
- HCPCS S2267 Induced abortion, 32 weeks/greater
- CPT 01964⁵ Anesthesia for abortion procedures
- CPT 01965 Anesthesia for incomplete or missed abortion procedures
- CPT 01966 Anesthesia for induced abortion procedures
- CPT 59840 Induced abortion, by dilation and curettage
- CPT 59841 Induced abortion, by dilation and evacuation
- CPT 59850 Induced abortion, by 1 or more intra-amniotic injections (amniocentesis-injections), including hospital admission and visits, delivery of fetus and secundines;
- CPT 59851 Induced abortion, by 1 or more intra-amniotic injections (amniocentesis-injections), including hospital admission and visits, delivery of fetus and secundines; with dilation and curettage and/or evacuation
- CPT 59852 Induced abortion, by 1 or more intra-amniotic injections (amniocentesis-injections), including hospital admission and visits, delivery of fetus and secundines; with hysterotomy (failed intra-amniotic injection)
- CPT 59855 Induced abortion, by 1 or more vaginal suppositories (eg, prostaglandin) with or without cervical dilation (eg, laminaria), including hospital admission and visits, delivery of fetus and secundines;
- CPT 59856⁶ Induced abortion, by 1 or more vaginal suppositories (eg, prostaglandin) with or without cervical dilation (eg, laminaria), including

⁵ CPT copyright 2022 American Medical Association. All rights reserved.

⁶ CPT copyright 2022 American Medical Association (AMA). All rights reserved.

hospital admission and visits, delivery of fetus and secundines; with dilation and curettage and/or evacuation

CPT 59857 Induced abortion, by 1 or more vaginal suppositories (eg, prostaglandin) with or without cervical dilation (eg, laminaria), including hospital admission and visits, delivery of fetus and secundines; with hysterotomy (failed medical evacuation)

Stillbirth

- O31.2--- Continuing pregnancy after intrauterine death of 1 fetus or more
- O36.4--- Maternal care for intrauterine death
- P95 Stillbirth
- Z37.1 Single stillbirth
- Z37.3 Twins, 1 liveborn and 1 stillborn
- Z37.4 Twins, both stillborn

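### The teratogen exclusion can remove a pregnancy because it ended in a misoprostol-coded induced termination, a secondary outcome

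*Protocol*

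**What the plan says.** Four places in the protocol have to be read together.

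- **Section 9.2.2** has one exclusion criterion: "Exposed to any known teratogens from 3 months prior to ECD through the end of the relevant exposure window". Exposure is found through NDCs or HCPCS codes, and the drug list is in Annex 2.
- **Section 9.2.5** fixes where each window stops. For the pregnancy window: "End date: End of the pregnancy". For the first-trimester window: "End date: End of the first trimester".
- **Annex 2, teratogen table,** lists misoprostol with no footnote. The table's one timing qualifier, "Exposure in 2nd or 3rd trimester", is attached to the angiotensin II receptor blockers.
- **Annex 2, induced-termination codes,** includes "HCPCS S0191 Misoprostal oral 200 mcg". The same list holds many codes that do not name misoprostol, for example "HCPCS S0199 Medically induced abortion by oral ingestion of medication including all associated services and supplies", Z33.2, and the ICD-10 and CPT abortion procedures.

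Induced termination is a secondary outcome. Section 8 makes estimating its risk in all three cohorts an unconditional objective; only the comparisons depend on sample size.

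**The concern.** Eligibility should not depend on the outcome. Here, one S0191 claim during pregnancy both identifies an induced termination and meets the exclusion criterion. A misoprostol dispensing found by NDC has the same excluding effect.

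The affected pregnancies leave both the numerator and the denominator. Induced-termination prevalence then comes out too low, and the prevalences of spontaneous abortion (SA), stillbirth and livebirth are calculated on a denominator that has lost terminations. If the share of terminations with a misoprostol claim differs between cohorts, the induced-termination prevalence ratio is also distorted.

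Nothing later in the protocol recovers these pregnancies. Medical record review (Section 9.3.1.3) and the analysis for unobserved outcomes (Section 9.7.4.3) apply to pregnancies already in the cohorts. The sensitivity analysis of malformations among non-livebirths promised in Section 9.9 would draw on the same depleted set.

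**Working it through.** **Text check.** For a pregnancy in the full-pregnancy window that ends in a termination carrying S0191:

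1. The claim falls on or before pregnancy end, so it lies inside the exclusion period.
2. It is a HCPCS claim for a listed drug, so it meets the criterion.
3. It is a listed induced-termination code, so it identifies the outcome.
4. No exception applies. The authors qualified one drug class by timing, and it was not this one.

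In the first-trimester window the same holds for claims up to the end of the first trimester. Later claims do not exclude.

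**Size for induced termination.** The protocol has no figure to reproduce. Inputs:

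- p = 0.18, from Section 9.5: "18% of pregnancies have historically been expected to end in induced termination".
- f = share of terminations with a misoprostol NDC or S0191 claim inside the window. This is not in the protocol and is varied here as an assumption.

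Observed prevalence = p(1 − f) / (1 − pf).

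| f | Pregnancies removed (0.18f) | Observed prevalence |
|---|---|---|
| 0 | 0 | 18.0% |
| 0.10 | 1.8% | 0.162 / 0.982 = 16.5% |
| 0.25 | 4.5% | 0.135 / 0.955 = 14.1% |
| 0.50 | 9.0% | 0.090 / 0.910 = 9.9% |

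**Effect on the other outcomes.** If only terminations are removed, every other prevalence is multiplied by 1 / (1 − 0.18f). At f = 0.50, the planned 14% for SA becomes 0.14 / 0.91 = 15.4%.

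If a share s of SAs also carries an excluding claim, observed SA = 0.14(1 − s) / (1 − 0.18f − 0.14s). This is below 14% only when s exceeds (0.18 / 0.86)f = 0.209f. Two assumed cases:

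- f = 0.6, s = 0.1: 0.126 / 0.878 = 14.4%, higher than planned.
- f = 0.6, s = 0.3: 0.098 / 0.850 = 11.5%, lower than planned.

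**Effect on the prevalence ratio for induced termination.**

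- True ratio 1, equal f in both cohorts: the ratio stays at 1.
- True ratio 1, f = 0.5 exposed and 0.4 comparator: 0.0989 / (0.108 / 0.928) = 0.85.
- True ratio 1, f = 0.5 exposed and 0.6 comparator: 0.0989 / (0.072 / 0.892) = 1.23.
- True ratio 2 (36% against 18%), f = 0.5 in both: (0.18 / 0.82) / 0.0989 = 2.22.

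**The case against.** The strongest reply has five parts.

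- **The loss is partial.** Many termination codes do not involve misoprostol. This stands: the undercount is selective by method of termination, and its size is unknown.
- **S0191 as an excluding code is inferred.** Annex 2 lists teratogens by drug name, and no exclusion code list is shown. This is true, but Section 9.2.2 says exposure is found by NDC or HCPCS code, and S0191 is a HCPCS code for a listed drug. A code list that omitted it would be an exception the protocol does not state.
- **The primary outcome is untouched.** Table 4 analyses major congenital malformation in linked livebirths, so terminations never enter that denominator. This stands. A reader might infer that the primary result is biased; this mechanism does not support that.
- **SA is a different case.** A reader might infer that SA prevalence is biased down in the same way. No misoprostol code is in the SA list, whether a claim for managing a loss falls inside the window depends on how pregnancy end is dated, and the working shows the direction can go either way.
- **Excluding teratogens through the etiologic window is deliberate.** This stands, and it limits the remedy. A reader might want the whole exclusion to stop at the index date. But PAXLOVID qualifies from 7 days before the estimated conception date (Section 9.2.6.1), and Section 9.3.3.1 foresees index dates before conception. For those pregnancies the rule would admit first-trimester teratogen exposure to the malformation analysis.

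**Conclusion.** The concern holds for induced termination. As written, the exclusion criterion and the outcome definition contradict each other, and pregnancies are removed because the outcome occurred. Prevalence is biased down for any f above zero: from 18% to 16.5%, 14.1% or 9.9% at f of 0.10, 0.25 or 0.50. These figures rest on the protocol's literature value of 18% and on assumed values of f.

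Three limits apply:

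- A null ratio is distorted only if f differs between cohorts, and the protocol gives no evidence that it does.
- The denominators for SA, stillbirth and livebirth are distorted, but the SA direction is open.
- An absolute livebirth shift should not be quoted. A reader might take livebirth as the residual 100 − 18 − 14 − 1 = 67%, but the protocol does not state that figure. Section 9.4.2 gives 80% of pregnancies with observed outcomes, and the divisors under Tables 1 and 2 imply 0.61 / 0.80 = 76%.

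The damage is to secondary outcomes, but their estimation is not conditional on sample size, so the contradiction should be resolved in the protocol.

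**What to change.** Reconcile Section 9.2.2 with the two Annex 2 lists. State that drug claims which identify or manage the end of the pregnancy do not count as teratogen exposure when they fall within a fixed, prespecified number of days of the recorded pregnancy end. This covers misoprostol, including S0191, and methotrexate when used to end the pregnancy. Leave the rest of the exclusion as it is for the malformation analysis.

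Add a sensitivity analysis of the pregnancy outcomes with the exclusion ended at the index date. This shows how much the remaining post-index exclusions matter without changing the malformation cohorts.

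The interim attrition flow charts in Section 9.7.1 could also report, by cohort, how many teratogen exclusions rest on misoprostol and how many of those carry a termination code. That would replace the assumed f with an observed one.

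The cost is a wording change, minor reprogramming of one criterion, and a few pregnancies retained whose misoprostol or methotrexate claims are ambiguous.

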9.2.3. Identification of pregnancy and estimation of LMP and ECD

Pregnancies will be identified using the Optum Dynamic Assessment of Pregnancies and Infants (DAPI) (Section 9.4.2). This process applies a set of algorithms comprised of International Classification of Diseases, 10th revision (ICD-10) diagnosis and procedure codes, Current Procedural Terminology¹ (CPT) codes, and HCPCS codes to the claims data to identify pregnancies, LMP date, pregnancy end date, and pregnancy outcome (Bertoia et al. 2022).

DAPI uses ICD-10 Z3A codes denoting weeks of gestation to estimate the LMP (Chomistek et al. 2021, Chomistek et al. 2022). The LMP date is the first day of the last menstrual period before pregnancy. Validation of Z3A-based LMP estimation has indicated good performance, with a median difference in days between LMP date based on Z3A codes and adjudicated (via medical record review) LMP date of 4.0 days (interquartile range: 2.0 – 10.0 days). Gestational age is anchored by the LMP date, where 12 weeks gestation is 12 completed weeks after LMP, 30 weeks gestation is 30 completed weeks after LMP, etc. Conception typically occurs about 2 weeks after the LMP date, around ovulation which is midway through the menstrual cycle. ECD will be calculated based on the estimated LMP (LMP + 14 days).

There is a small fraction of pregnancies that do not have Z3A codes; in these cases, DAPI assigns an average length of gestation for different pregnancy outcomes and uses that average length to estimate the accompanying ECD (eg, 39 weeks for full-term births and 10 weeks for all abortions), as described by Hornbrook et al. (Hornbrook et al. 2007). DAPI may be refined over the course of the project based on clinical input and review of published literature.

¹ CPT copyright 2022 American Medical Association (AMA). All rights reserved.

Fee schedules, relative value units, conversion factors and/or related components are not assigned by the AMA, are not part of CPT, and the AMA is not recommending their use. The AMA does not directly or indirectly practice medicine or dispense medical services. The AMA assumes no liability for data contained or not contained herein.

CPT is a registered trademark of the American Medical Association.

9.2.4. Identification of COVID-19 episodes

[figure not shown]
COVID-19 episodes will be identified through presence of the ICD-10 diagnosis code:

• U07.1 (COVID-19, virus identified [lab confirmed])

A recent paper found adequate validity when using ICD-10 diagnosis code U07.1 to identify hospitalized COVID-19 patients in 2020, with PPVs ranging from 70% to 93% in nationally insured patients (Kluberg et al. 2022).

Episodes of COVID-19 will be defined by clustering all COVID-19 diagnoses occurring within 14 days of one another, reflecting the upper range of the incubation period (WHO 2023). Because the duration of symptomatic COVID-19 is variable, a grace period of 14 days following the final COVID-19 diagnosis within a cluster will be added to conservatively capture the symptomatic duration of a single COVID-19 episode (Sudre et al. 2021) (Figure 3).

Figure 3. Example Pregnancy with Two Episodes of COVID-19

The frequency, duration and timing of COVID-19 episodes will be described. Eligibility for the overall study population will not be restricted based on the presence of COVID-19 during pregnancy or in proximity to COVID-19 treatments; rather, the frequency and characteristics of COVID-19 episodes will be summarized and described and may be used for subgroup analysis. COVID-19 episodes will be defined independently of any treatment(s) received for COVID-19; however, treatments received during COVID-19 episodes will be characterized with regard to the COVID-19 episode during which they occur (eg, time from COVID-19 diagnosis to treatment initiation, inpatient status at time of COVID-19 diagnosis, etc.; Section 9.3.3).

9.2.5. Exposure windows

From the base population, qualifying pregnancies will be classified according to the COVID-19 treatment received during the following relevant exposure windows:

- First trimester exposure window
 - o Start date: ECD therapy-specific window
 - o End date: End of the first trimester

• Pregnancy exposure window

o Start date: ECD – therapy-specific window

End date: End of the pregnancy

As different COVID-19 therapies will have varying rates of elimination, the length of each relevant exposure window will be extended (prior to the ECD) by a corresponding therapy-specific window, based on the indicated treatment duration (plus a grace period for self-administered drugs) and the time to non-detectable concentration in the body (defined as 5x the clearance half-life). This ensures the capture of exposure to COVID-19 therapies administered or dispensed prior to the ECD but which remain in the body at ECD. Sections 9.2.6.1 and 9.2.6.2 describe the therapy-specific windows for each of the study therapies.

9.2.6. Study cohorts

Three mutually exclusive study exposure cohorts will be created based on received COVID-19 treatment during each exposure window (first trimester, pregnancy) for a total of 6 study cohorts:

- Cohort 1 (PAXLOVID cohorts): at least 1 dispensing of PAXLOVID within the relevant exposure window, and no evidence of comparator medications within the relevant exposure window
- Cohort 2 (Treated Comparator Only cohorts): no evidence in the study database of a dispensing of PAXLOVID, and dispensing or administration of the following treatments indicated for the treatment of mild-to-moderate COVID-19 within the relevant exposure window
 - Remdesivir
 - Bebtelovimab
- Cohort 3 (Untreated Comparator cohorts): evidence of a COVID-19 diagnosis, and no evidence in the study database of a dispensing or administration of any COVID-19 treatments within the relevant exposure window

9.2.6.1. Cohort 1: PAXLOVID cohorts

Pregnancies will be included in the PAXLOVID cohorts (Cohort 1) if they meet the following criteria:

1. Dispensing of outpatient PAXLOVID between 7 days prior to ECD and the end of the exposure window.

AND

- 2. None of the following:
 - a. Administration of remdesivir between 9 days prior to ECD and the end of the exposure window.

OR

b. Administration of bebtelovimab between 60 days prior to ECD and the end of the exposure window.

The 7-day pre-ECD window for PAXLOVID was chosen because of the 5-day recommended treatment course, plus 2 days to achieve 5x the clearance half-life. See Section 9.2.6.2 for justification for other pre-ECD windows.

Because the precise indication for PAXLOVID ("mild-to-moderate COVID-19") cannot be directly captured in claims data, and to improve comparability with comparator pregnancies, only PAXLOVID dispensings occurring in an outpatient setting will be eligible for inclusion.

